5.1.3 Baseline (Visit 3)

Pre-Conditioning (Assessment C)

After BM harvest and if the autologous OTL-101 product has met the release criteria ([Section 3.7.1](#)), additional baseline samples must be collected for the following tests within 1 week before the first administration of Busulfan:

- Physical examination, including vital signs (temperature, pulse rate, respiratory rate and blood pressure). Temperature can be measured as per standard clinic practice,

- Hematology (see [Table 3](#)),
- Prothrombin or INR and PTT,
- Biochemistry (see [Table 3](#)),
- Serum HCG (pregnancy test) if female of child-bearing age (and if more than 28 days have elapsed since the screening test),
- Urinalysis,
- Pulse oximetry,
- Interval history (including routine review of systems, including infectious symptoms (e.g., fever), AEs and concomitant medications),
- Measurement of immune function:
 - Absolute numbers of CD3+, CD4+ and CD8+ T-lymphocytes, CD19+ B-lymphocytes and CD56+/CD16+ (or CD56+/CD3-) NK cells, CD4+/CD45RA+ (naïve) and CD4+/CD45RO+ (memory) T cells,
 - TREC levels,
 - TCR V β usage,
 - lymphocyte response to phytohemagglutinin (PHA) (if sufficient cells),
 - Serum immunoglobulin (IgG, IgA, IgM).

Please note: the above immune function tests can be performed at any point after provision of consent/assent and prior to Busulfan administration in younger subjects if deemed appropriate by the Investigator.

- Peripheral blood mononuclear cells (PBMC) and serum banking for RCL determination. These tests can be performed at any time following BM harvest (Visit 2: Assessment B) and prior to OTL-101 administration (Visit 3: Assessment F) in younger subjects if deemed appropriate by the Investigator.
- Measurements of erythrocyte ADA enzymatic activity and erythrocyte deoxyadenine nucleotide levels. These tests can be performed at any time following BM harvest (Visit 2: Assessment B) and prior to OTL-101 administration (Visit 3: Assessment F) in younger subjects if deemed appropriate by the Investigator.

The Investigator must ensure a PICC line or central venous catheter is in place prior to the start of Busulfan conditioning.

5.1.4 Busulfan Conditioning (Visit 3)

These visits will be performed as part of the subject's hospital admission at Visit 3 (Baseline). Two doses of Busulfan will be administered to the subject as follows:

Day -4 to -3 (Assessment D): The subject's weight will be recorded to calculate the dose of Busulfan. Busulfan will be administered intravenously at a dose of 3 mg/kg infused over 3 hours. Blood samples will be taken immediately at the end of the infusion, and then +1, 2, 4, 8, and 13 hours after the end of infusion, in order to calculate the AUC. These samples may be drawn +/-15 minutes of the time-point, but the actual time with reference to the administration

of Busulfan should be recorded to enable an accurate AUC calculation. Adverse events and concomitant medications will be recorded.

Day -2 to -1 (Assessment E): Busulfan dose adjusted for AUC taken on Day -3. The clinical pharmacist will calculate the AUC from the first dose of Busulfan based on the measured serum levels, to calculate the amount needed for second dose to reach total net AUC of 4,900 (this is equivalent to 20mg*h/L) (see [Section 6.2.1.1](#)). Blood samples will be taken before the second infusion (to confirm the previous Busulfan has cleared the blood), immediately at the end of the infusion, and then +1, 2, 4, 8, and 13 hours after the end of infusion, in order to re-calculate the AUC. These samples may be drawn +/-15 minutes of the time-point, but the actual time with reference to the administration of Busulfan should be recorded to enable an accurate AUC calculation. The PK samples will ensure the subject receives the minimum acceptable dose to achieve good engraftment but at the same time minimising the exposure to the conditioning regimen. The tailoring of conditioning treatment is only made possible by using the cryopreserved formulation within this protocol due to the prolonged stability. Adverse events and concomitant medications will be recorded.

Dose Calculation

The calculated AUC from the first Busulfan dose is inserted into the formula below to determine the amount of Busulfan required for the second dose in mg/kg.

$(\text{1st dose (mg/kg)}) / \text{Calculated 1st dose AUC} = (\text{Total Dose (mg/kg)}) / [\text{Target AUC (4,900 uM*min)}]$

$(\text{1st dose (mg/kg)}) / \text{Calculated 1st dose AUC} \times \text{Target AUC (4,900)} = (\text{Total dose (mg/kg)})$

$(\text{1st dose (mg/kg)}) \times (\text{Target AUC(4,900)}) / \text{Calculated 1st dose AUC} = (\text{Total dose (mg/kg)})$

Calculated total dose (mg/kg) – 1st dose (mg/kg) = 2nd dose (mg/kg).

For example 1st dose = 3 mg/kg and the AUC = 3,200 uM*min

$3 \text{ mg/kg} \times 4,900 / 3,200 = 4.6 \text{ mg/kg}$ total dose.

$4.6 \text{ mg/kg} - 3.0 \text{ mg/kg} = 1.6 \text{ mg/kg}$ for second dose.

AUC is calculated from serum Busulfan level values using pKsolver³.

5.1.5 OTL-101 Administration (Visit 3)

This visit will be performed as part of the subject's hospital admission at Visit 3 (Baseline) and following completion of the conditioning regimen.

Day 0 - day of transplantation (Assessment F)

- Before administration of OTL-101;

³ (<https://www.ncbi.nlm.nih.gov/pubmed/20176408>) Zhang Y1, Huo M, Zhou J, Xie S. PKSolver: An add-in program for pharmacokinetic and pharmacodynamic data analysis in Microsoft Excel. Comput Methods Programs Biomed. 2010 Sep;99(3):306-14. PMID: 20176408

- The subject will be pre-medicated with an appropriate dosage of acetaminophen (e.g., 10 to 15 mg/kg orally), and diphenhydramine (e.g., 0.5 to 1.0 mg/kg intravenous or orally), 15 to 90 minutes prior to infusion.
- Steroids and anticonvulsants will be prepared before infusion and ready to infuse if necessary.
- Serum HCG (pregnancy test) if female of child-bearing age must be performed prior to infusion.
- Monitoring before, during and after the intravenous infusion, as per institution standards, of vital signs and adverse events, including allergic reaction(s). Subjects are required to be closely monitored for signs of allergic reactions/immune reactions, by looking at clinical parameters (fever, rash, difficulties to breath, tremors, tachycardia, arrhythmias).
- Administration of OTL-101 product (Day 0) at least 24 hours after the end of the infusion of the last dose of non-myeloablative conditioning (Busulfan). For administration instructions see [Section 17: Appendix 1](#).
- Adverse events and concomitant medications will be recorded.

5.1.6 Immediate Post-transplant Tests and Care (Visit 3)

These visits will be performed as part of the subject's hospital admission which commenced at the baseline visit (Visit 3). During the first month after administration of the OTL-101 treatment, the following tests will be performed on the day after treatment (Day 1) and then twice weekly thereafter.

These visits may be performed +/- 2 days from the scheduled date.

Post-transplant (Assessments G to M)

- Interval history (including routine review of systems, including infectious symptoms (e.g., fever), AEs and concomitant medications),
- Hematology (see [Table 3](#)),
- Biochemistry (see [Table 3](#)).

The subjects will be kept in hospital for close monitoring for up to 24 days post OTL-101 infusion. However, they may be kept in for longer if this is deemed clinically necessary and depending on the medical care they require (e.g. central venous catheter care, infections, protective isolation, nutritional support), the consequences of toxicity due to Busulfan, the engraftment of transduced cells, and immune reconstitution. Alternatively, for subjects who are not geographically close to the clinical site who are clinically stable, post-transplant care may be transferred to the home physician provided the identified clinician agrees to assume this post-transplant monitoring. The home physician will be asked to record all protocol specific assessments on a form provided. This data will be transmitted to the Investigator for data entry into the eCRF. Monitoring can be assured as either an in-patient or out-patient. In the latter case, the subject will stay in hospital for a minimum of 3 days after OTL-101 infusion at the investigational site treatment facility, before being transferred. This planned discharge and subsequent readmission to a second facility would not meet the criteria for being reported as a SAE.

After the transplant, the subject will be maintained on prophylactic antibiotics and intravenous gamma-globulin replacement as needed and/or as per institutional procedures, and will be closely monitored. Any concomitant medication administered to the subject should be recorded in the eCRF. A subject will be readmitted to hospital when deemed clinically necessary. These reasons include, but are not limited to: fever and neutropenia, bacteremia, possible central venous access device infection, or other infections that require initial parenteral antibiotics, organ failure, extreme adverse social situations, and/or bleeding.

5.1.7 Follow-Up (Visits 4 to 11)

Following discharge from the hospital after transplantation, follow-up visits will be performed to determine whether the genetically modified cells have engrafted and are able to produce mature lymphoid and hematopoietic cells containing and expressing the *ADA gene*, and the extent and time-course of immune reconstitution.

The subjects will be evaluated at the following time-points: Month 1, 3, 6, 9, 12, 18, and 24 (end of study visit). Because of the large number of blood tests planned and the limited volumes of blood that can be obtained from young children, it may not be possible to perform every scheduled investigation listed below at each time-point. Therefore, the priority for the ranking of blood tests will be as per the order presented for each visit. The following examinations will be performed:

Month 1/Day 30 (Visit 4 - +/- 1 week)

- Physical examination, vital signs, height, weight and interval history (including routine review of systems, including infectious symptoms (e.g., fever), AEs and concomitant medications),
- Use of PEG-ADA and IgG replacement therapy will be documented. Please note PEG-ADA administration will be stopped at this visit,
- Hematology and biochemistry panels,
- Monitoring for severe infections and/or opportunistic infectious episodes at each study visit,
- Immune function testing;
 - o Determination of absolute numbers of CD3+, CD4+ and CD8+ T-lymphocytes, CD19+ B-lymphocytes and CD56/CD16+ (or CD56+/CD3-) NK cells, CD4+/CD45RA+ (naïve) and CD4+/CD45RO+ (memory) T cells,
 - o Serum immunoglobulin (IgG, IgA, IgM).
- Gene transduction/expression;
 - o Measurement of ADA expression in erythrocytes by ADA enzymatic assay and deoxyadenine nucleotides in RBC.

Day 42 (Visit 5 - +/- 1 week)

The Day 42 assessment will use laboratory parameters to confirm if hematologic reconstitution has occurred. A failure of hematologic reconstitution is defined as persistent ANC < 200/ μ l or platelets < 20,000/ μ l on three independent and consecutive determinations over at least ten days after day 42 from the day of cell infusion. If hematologic reconstitution has not taken place by Day 42 the backup HSC sample will be processed according to the instructions in [Section 3.7](#)

PROTOCOL AMENDMENT 4: VERSION 5.0, 28 MARCH 2018

PAGE 54/130

and re-infused to overcome more severe myelosuppressive effects of the conditioning regimen. If the failure of hematologic reconstitution persist after the back-up marrow has been given through day 90 from the initial infusion of the cell product, prolonged unresponsive pancytopenia will exist.

If the Investigator considers the use of the back up HSC sample is not in the best interests of the subject, rescue medication, as per standard institute protocols, will be implemented. Any treatment administered to the subject will be recorded in the eCRF. Adverse events will also be recorded.

Month 3 (Visit 6 - +/- 2 weeks)

- Physical examination, vital signs, height, weight and interval history (including routine review of systems, including infectious symptoms (e.g., fever), AEs and concomitant medications),
- Assessment of re-initiation of PEG-ADA therapy and use of IgG replacement therapy will be documented. Please note: subjects should have discontinued PEG-ADA treatment at Visit 4 (Month 1/Day 30),
- Hematology and biochemistry panels,
- RCL assay in PBMC,
- Serum to be banked for possible Western blot testing for RCL (testing performed if the RCL assay in PBMC returns a positive result),
- Monitoring for severe infections and/or opportunistic infectious episodes at each study visit,
- Vector integration analysis,
- Immune function testing:
 - o Determination of absolute numbers of CD3+, CD4+ and CD8+ T-lymphocytes, CD19+ B-lymphocytes and CD56/CD16+ (or CD56+/CD3-) NK cells, CD4+/CD45RA+ (naïve) and CD4+/CD45RO+ (memory) T cells:
 - o Serum immunoglobulin (IgG, IgA, IgM),
- Gene transduction/expression:
 - o Measurement of the proportion of cells containing the inserted *ADA gene* in PBMC and granulocytes and/or lineage-sorted cells,
 - o Measurement of ADA expression in erythrocytes by ADA enzymatic assay and deoxyadenine nucleotides in RBC.

Month 6 (Visit 7 - +/- 2 weeks)

- Physical examination, vital signs, height, weight and interval history (including routine review of systems, including infectious symptoms (e.g., fever), AEs and concomitant medications),
- Evaluation of quality of life using the Karnofsky/Lansky scale and questions relevant to general well-being, school attendance, and ability to practice sports, respectively,
- Assessment of re-initiation of PEG-ADA therapy and use of IgG replacement therapy will be documented. Please note: subjects should have discontinued PEG-ADA treatment at Visit 4 (Month 1/Day 30),
- Assessment of the success of treatment at the subject level (“responder analysis”) at 6 months post OTL-101 infusion, by evaluating:
 - a) Evidence of erythrocyte ADA enzyme activity above baseline/pre-treatment level (>0 Units),
 - b) Evidence of immune reconstitution (absolute number of CD3 cells $\geq 200/\text{mm}^3$),
 - c) Detectable gene-marked granulocytes by differential polymerase chain reaction (dPCR)/qPCR ($\geq 1/10,000$ cells).

If there is no evidence of hematopoietic reconstitution, subjects will require PEG-ADA and/or allogenic HSCT, if available and deemed appropriate by the Investigator. The definition applied for lack of hematopoietic reconstitution is the failure to meet ALL three criteria listed above (a-c). Any subject not meeting any of these three criteria will be deemed a treatment failure and should be withdrawn from the study as described in [Section 3.6.1](#).

- Hematology and biochemistry panels,
- RCL assay in PBMC,
- Serum to be banked for possible Western blot testing for RCL (testing performed if the RCL assay in PBMC returns a positive result),
- Monitoring for leukemia (by nrLAM-PR) if the criteria for triggering nrLAM-PCR are fulfilled. A blood sample will be taken unless clinical/hematologic findings indicate potential leukoproliferation, whereby a bone marrow sample will be required,
- Monitoring for severe infections and/or opportunistic infectious episodes at each study visit,
- Vector integration analysis,
- Immune function testing:
 - o Determination of absolute numbers of CD3+, CD4+ and CD8+ T-lymphocytes, CD19+ B-lymphocytes and CD56/CD16+ (or CD56+/CD3-) NK cells, CD4+/CD45RA+ (naïve) and CD4+/CD45RO+ (memory) T cells,
 - o T-cell proliferative responses to PHA,
 - o Measurement of serum immunoglobulin levels (IgG, IgA, IgM) if not receiving immunoglobulins,

PROTOCOL AMENDMENT 4: VERSION 5.0, 28 MARCH 2018

PAGE 56/130

- TREC,
- TCR V β usage,
- Gene transduction/expression;
 - Measurement of the proportion of cells containing the inserted *ADA gene* in PBMC and granulocytes and/or lineage-sorted cells,
 - Measurement of ADA expression in erythrocytes by ADA enzymatic assay and deoxyadenine nucleotides in RBC.

Month 9 (Visit 8 - +/- 2 weeks)

- Physical examination, vital signs, height, weight and interval history (including routine review of systems, including infectious symptoms (e.g., fever), AEs and concomitant medications),
- Assessment of re-initiation of PEG-ADA therapy and use of IgG replacement therapy will be documented. Please note: subjects should have discontinued PEG-ADA treatment at Visit 4 (Month 1/Day 30),
- Hematology and biochemistry panels,
- Monitoring for severe infections and/or opportunistic infectious episodes at each study visit,
- Immune function testing;
 - Determination of absolute numbers of CD3+, CD4+ and CD8+ T-lymphocytes, CD19+ B-lymphocytes and CD56/CD16+ (or CD56+/CD3-) NK cells, CD4+/CD45RA+ (naïve) and CD4+/CD45RO+ (memory) T cells;
 - T-cell proliferative responses to PHA,
 - Serum immunoglobulin (IgG, IgA, IgM),
- Gene transduction/expression;
 - Measurement of ADA expression in erythrocytes by ADA enzymatic assay and deoxyadenine nucleotides in RBC.

Month 12 (Visit 9 - +/- 4 weeks)

- Physical examination, vital signs, height, weight and interval history (including routine review of systems, including infectious symptoms (e.g., fever), AEs and concomitant medications),
- Evaluation of quality of life using the Karnofsky/Lansky scale and questions relevant to general well-being, school attendance, and ability to practice sports, respectively,
- Assessment of re-initiation of PEG-ADA therapy and use of IgG replacement therapy will be documented. Please note: subjects should have discontinued PEG-ADA treatment at Visit 4 (Month 1/Day 30),
- Hematology and biochemistry panels,
- RCL assay in PBMC,

- Serum to be banked for possible Western blot testing for RCL (testing performed if the RCL assay in PBMC returns a positive result),
- Vector integration analysis,
- Monitoring for leukemia (by nrLAM-PR) if the criteria for triggering nrLAM-PCR are fulfilled. A blood sample will be taken unless clinical/hematologic findings indicate potential leukoproliferation, whereby a bone marrow sample will be required,
- Monitoring for severe infections and/or opportunistic infectious episodes at each study visit,
- Immune function testing:
 - o Determination of absolute numbers of CD3+, CD4+ and CD8+ T-lymphocytes, CD19+ B-lymphocytes and CD56/CD16+ (or CD56+/CD3-) NK cells, CD4+/CD45RA+ (naïve) and CD4+/CD45RO+ (memory) T cells;
 - o T-cell proliferative responses to PHA,
 - o Measurement of serum immunoglobulin levels (IgG, IgA, IgM) if not receiving immunoglobulins,
 - o Measurement of specific antibodies to tetanus toxoid only if subjects have stopped immunoglobulin replacement and have received tetanus vaccination,
 - o TREC,
 - o TCR V β usage,
- Gene transduction/expression:
 - o Measurement of the proportion of cells containing the inserted *ADA* gene in PBMC and granulocytes and/or lineage-sorted cells,
 - o Measurement of ADA expression in erythrocytes by ADA enzymatic assay and deoxyadenine nucleotides in RBC.

Month 18 (Visit 10 - +/- 4 weeks)

- Physical examination, vital signs, height, weight and interval history (including routine review of systems, including infectious symptoms (e.g., fever), AEs and concomitant medications),
- Evaluation of quality of life using the Karnofsky/Lansky scale and questions relevant to general well-being, school attendance, and ability to practice sports, respectively,
- Assessment of re-initiation of PEG-ADA therapy and use of IgG replacement therapy will be documented. Please note: subjects should have discontinued PEG-ADA treatment at Visit 4 (Month 1/Day 30),
- Hematology and biochemistry panels,
- Monitoring for leukemia (by nrLAM-PR) if the criteria for triggering nrLAM-PCR are fulfilled. A blood sample will be taken unless clinical/hematologic findings indicate potential leukoproliferation, whereby a bone marrow sample will be required,

PROTOCOL AMENDMENT 4: VERSION 5.0, 28 MARCH 2018

PAGE 58/130

- Monitoring for severe infections and/or opportunistic infectious episodes at each study visit,
- Vector integration analysis,
- Immune function testing;
 - o Determination of absolute numbers of CD3+, CD4+ and CD8+ T-lymphocytes, CD19+ B-lymphocytes and CD56/CD16+(or CD56+/CD3-) NK cells, CD4+/CD45RA+ (naïve) and CD4+/CD45RO+ (memory) T cells,
 - o T-cell proliferative responses to PHA,
 - o Serum immunoglobulin (IgG, IgA, IgM),
 - o Measurement of specific antibodies to tetanus toxoid only if subjects have stopped immunoglobulin replacement and have received tetanus vaccination.
 - o TREC,
 - o TCR V β usage.
- Gene transduction/expression;
 - o Measurement of ADA expression in erythrocytes by ADA enzymatic assay and deoxyadenine nucleotides in RBC.

Month 24 (Visit 11 - +/- 4 weeks)

- Physical examination, vital signs, height, weight and interval history (including routine review of systems, including infectious symptoms (e.g., fever), AEs and concomitant medications),
- Evaluation of quality of life using the Karnofsky/Lansky scale and questions relevant to general well-being, school attendance, and ability to practice sports, respectively,
- Assessment of re-initiation of PEG-ADA therapy and use of IgG replacement therapy will be documented. Please note: subjects should have discontinued PEG-ADA treatment at Visit 4 (Month 1/Day 30),
- Hematology and biochemistry panels,
- RCL assay in PBMC,
- Serum to be banked for possible Western blot testing for RCL (testing performed if the RCL assay in PBMC returns a positive result),
- Vector integration analysis,
- Monitoring for leukemia (by nrLAM-PR) if the criteria for triggering nrLAM-PCR are fulfilled. A blood sample will be taken unless clinical/hematologic findings indicate potential leukoproliferation, whereby a bone marrow sample will be required,
- Monitoring for severe infections and/or opportunistic infectious episodes at each study visit,
- Immune function testing;

- Determination of absolute numbers of CD3+, CD4+ and CD8+ T-lymphocytes, CD19+ B-lymphocytes and CD56/CD16+ (or CD56+/CD3-) NK cells, CD4+/CD45RA+ (naïve) and CD4+/CD45RO+,(memory) T cells
- T-cell proliferative responses to PHA,
- Serum immunoglobulin (IgG, IgA, IgM),
- Measurement of specific antibodies to tetanus toxoid only if subjects have stopped immunoglobulin replacement and have received tetanus vaccination,
- TREC,
- TCR V β usage,
- Gene transduction/expression;
 - Measurement of the proportion of cells containing the inserted *ADA gene* in PBMC and granulocytes and/or lineage-sorted cells.
 - Measurement of ADA expression in erythrocytes by ADA enzymatic assay and deoxyadenine nucleotides in RBC.

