9.3.1 Primary Efficacy Endpoints

The primary efficacy endpoints for this study include treatment success at 6 months post OTL-101 infusion, and overall survival and event-free survival at 12 months post OTL-101 infusion.

Treatment success at 6 months post OTL-101 infusion, will be performed in support of CMC assessing comparability between cryopreserved and fresh formulations. Evaluation of the success of therapy will be based on the following parameters and their thresholds:

- a) Erythrocyte ADA enzyme activity above baseline/pre-treatment level (>0 Units),
- b) Absolute CD3+ T-cell counts $\geq 200/\text{mm}^3$, and
- c) Peripheral blood samples positive for vector sequences by qPCR($\geq 1/10,000$ cells).

Treatment will be deemed successful in subjects meeting all three above thresholds. These subjects will be designated as “responders”. Those subjects failing to meet at least one of the above thresholds will be considered to be “non-responders.”

Overall Survival is defined as the time-to death from the OTL-101 infusion if death occurred, or to the date of the last evaluation if death did not occur. If no death occurred, the subject’s data will be considered censored at the last evaluation.

Event Free Survival is defined as the time-to event from the OTL-101 infusion if an event occurred, or to the date of the last evaluation without an event if no event occurred. If no event occurred, the subject’s data will be considered censored at the last evaluation. Event is defined as any of the following:

- Death
- Returning to PEG-ADA ERT
- Need of rescue HSCT

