8.3 Efficacy Evaluations

8.3.1 Primary Efficacy Endpoints

8.3.1.1 Response to OTL-101 Treatment at 6 Months

Response to OTL-101 treatment at 6 months post administration will be based on the following criteria:

- ADA activity in red blood cells: change from baseline >0 Units,
- Absolute CD3+ T-cell count $\geq 200/\text{mm}^3$, and
- Detectable gene-marked granulocytes by differential polymerase chain reaction (dPCR)/qPCR $\geq 1/10,000$ cells.

Subjects who meet all three criteria will be said to have mounted a response.

For any subjects with missing values at 6 months, the earliest assessments after month 6 will be used. In addition, if ADA activity at baseline is not available, any positive value will be considered as a positive response.

The number (%) of subjects mounting a response will be summarized and descriptively compared with the proportion from the UCLA “Fresh” study. In addition, the number (%) of subjects with a response to each of the individual criteria will be summarized.

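### At Month 6 the blood-test ranking can drop two primary-endpoint assays (gene marking and erythrocyte ADA) before exploratory ones, and the protocol does not say which list entry sets the rank

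*Protocol*

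**What the plan says.** Protocol 5.1.7 warns that, because young children can give little blood, "it may not be possible to perform every scheduled investigation listed below at each time-point". It resolves the shortage with a rule: "the priority for the ranking of blood tests will be as per the order presented for each visit". Protocol 5.1.8 repeats the rule for the early termination visit.

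The Month 6 list refers to the responder components in two places.

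- The fourth bullet, above every blood panel, calls for assessing treatment success "at 6 months post OTL-101 infusion, by evaluating" erythrocyte ADA activity, CD3 count and gene-marked granulocytes against their thresholds.
- The assays themselves come further down. The CD3 count sits in the first immune-function entry ("Determination of absolute numbers of CD3+, CD4+ and CD8+ T-lymphocytes, CD19+ B-lymphocytes" and other subsets). The last two entries are the proportion of cells carrying the inserted gene "in PBMC and granulocytes and/or lineage-sorted cells" and then "Measurement of ADA expression in erythrocytes by ADA enzymatic assay and deoxyadenine nucleotides in RBC".

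All three components are needed for response. Protocol 9.3.1 states: "Treatment will be deemed successful in subjects meeting all three above thresholds". If a Month 6 value is missing, SAP 8.3.1.1 says that "the earliest assessments after month 6 will be used".

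**The concern.** A priority rule for scarce blood should protect the primary endpoint. Read by its assay entries, this list does the reverse: erythrocyte ADA would be given up first and gene marking second, while PHA, TREC and TCR V-beta, which Protocol 7.1.3 classes as exploratory, would be kept. The responder bullet might be meant to prevent that, but nothing says so.

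At stake is the 6-month responder comparison with the fresh formulation, in a study of 10 subjects whose first analysis may include as few as 5. The rule is written for young children with limited blood, so any loss would be expected mainly in the smallest subjects. A lost assay would either move that subject's result to a later visit or, if no later value exists at the data cut, leave the subject without a classification rule.

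**Working it through.** **1. The Month 6 blood-related entries, in listed order** (Protocol 5.1.7; roles from Protocol 3.2.3, 7.1 and 8.1)

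| Order | Entry | Role |
|---|---|---|
| 1 | Hematology and biochemistry | Safety |
| 2 | RCL assay | Safety |
| 3 | Serum banked for RCL | Safety |
| 4 | Leukemia monitoring, if triggered | Safety |
| 5 | Vector integration | Exploratory, but bears on monoclonal expansion |
| 6 | Lymphocyte subsets, including CD3 | **Primary component** |
| 7 | PHA response | Exploratory |
| 8 | Immunoglobulins, if not on replacement | Exploratory |
| 9 | TREC | Exploratory |
| 10 | TCR V-beta | Exploratory |
| 11 | Gene marking | **Primary component** |
| 12 | Erythrocyte ADA and deoxyadenine nucleotides | **Primary component** |

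Two of the three components hold the last two places. CD3 is already directly below the safety tests.

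**2. Does the responder bullet set the rank?** Three features suggest that it is a classification and not a draw.

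- It compares results with thresholds and then states what follows from failure.
- Protocol Table 2 gives the responder assessment its own row, separate from the rows for the ADA assay and for presence of the ADA gene, both of which are also marked at Month 6.
- The Month 3 list has no responder bullet and ends with the same two assays.

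On the other side, the bullet names all three components and even the PCR method for one of them, and it stands above every blood panel. The text does not settle the matter.

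**3. What the SAP fallback would use.** Protocol Table 2 schedules the ADA assay at Months 1, 3, 6, 9, 12, 18 and 24, and gene marking at Months 3, 6, 12 and 24 (both also at early termination). The next scheduled values are therefore:

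- ADA: Month 9, which is 9 − 6 = 3 months late.
- Gene marking: Month 12, which is 12 − 6 = 6 months late.

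The Month 9 list also puts ADA last, and the Month 12 list also ends with gene marking and ADA, so the fallback draw is subject to the same ranking. SAP 8.3.1.1 has no rule for a subject with no later value. SAP 6 allows the first analysis once at least 5 subjects have completed 6 months, when some may have none.

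**4. Size.** One subject is 1/10 = 10% of the denominator at n=10 and 1/5 = 20% at n=5.

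Protocol 9.4 gives 15% as the half-width of the exact 95% interval at 100% success with N=10. With all n responding, the lower limit is 0.025^(1/n). For n=10 it is 0.025^(1/10) = 69.2%, so the half-width is (100 − 69.2)/2 = 15.4%, which reproduces the stated 15%. The plan attaches exact intervals to survival, not to the responder proportion, so the next figures only illustrate scale (Clopper-Pearson):

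| Case | Interval | Half-width |
|---|---|---|
| 10/10 | 69.2–100% | 15.4% |
| 9/9 (one subject excluded) | 66.4–100% | 16.8% |
| 9/10 (one counted as non-responder) | 55.5–99.7% | 22.1% |
| 5/5 | 47.8–100% | 26.1% |
| 4/4 (one excluded) | 39.8–100% | 30.1% |
| 4/5 (one counted as non-responder) | 28.4–99.5% | 35.6% |

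No missing-data rate is given. If each subject independently had a 5%, 10% or 20% chance of losing a component (assumed values), the chance of at least one loss among 10, 1 − (1 − q)^10, would be 40%, 65% or 89%. Among 5 it would be 23%, 41% or 67%.

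**The case against.** The strongest reply is that the responder bullet, taken literally, already ranks the three components above every blood panel. That reading is possible. It does not remove the problem, because a priority rule with two readings for a primary endpoint still needs one sentence to settle it.

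Competition for blood is also not demonstrated. Only a total of 15 to 90 ml per visit is given (Protocol 8.7). Under Protocol 7.2, granulocytes come from the same Ficoll-Hypaque separation as the PBMC, and ADA is measured in red cells, so dropping one assay may not free blood for another. Two entries in the queue are conditional. These points stand as limits on how often a loss would occur. They do not justify the order.

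Sites also have good reason to obtain these samples: the Month 6 result decides responder status and counts toward the three-non-responder rule in Protocol 3.6.1. That makes loss less likely, but it relies on sites departing from a literal reading of the assay list.

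Finally, the SAP fallback means a missed assay need not be a lost endpoint. It is not restricted to scheduled visits, and Protocol 2.1 reports granulocyte marking and red-cell ADA stable after about Month 3 with the fresh product. A later value may often give the same classification. But that plateau was observed with the fresh product, and the responder analysis exists to compare the cryopreserved product with it.

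**Conclusion.** The point holds as an ambiguous priority rule which, on its better reading, can drop two primary-endpoint assays before exploratory ones. Each affected subject is 10% of the denominator at n=10 or 20% at n=5, with a fallback 3 months late for ADA and 6 months late for gene marking if only scheduled visits supply it. The frequency of loss cannot be estimated from the documents. No sample-size or precision figure in the plan depends on this point.

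A reader might infer three stronger things that the documents do not support.

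- That these assays are certain to be the first lost. This follows only if the assay entries set the rank, and the responder bullet leaves another reading open.
- That baseline ADA at Visit 3 needs the same reordering. Protocol 5.1.3 lists it last among the blood tests but contains no ranking rule, and it already gives younger subjects a flexible window between harvest and infusion.
- That the primary assays should outrank vector integration because it is listed as exploratory. Monoclonal expansion is a safety concern (Protocol 3.2.3, 8.1) and a halting criterion whose investigation includes proviral integration analysis (Protocol 3.6.1).

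**What to change.** In the Month 6 list of Protocol 5.1.7, place the CD3 count, granulocyte qPCR and erythrocyte ADA directly after the safety tests (hematology, biochemistry, RCL, triggered leukemia monitoring and vector integration) and ahead of PHA, TREC and TCR V-beta. Since CD3 is already there, only two entries move. Add a sentence saying that the assay entries, not the responder bullet, set the sampling rank. The sponsor may wish to use the same order at Months 9 and 12, which supply the fallback values.

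The cost is a short protocol edit with no change to design, sample size or analysis. If blood runs short, PHA, TREC and TCR V-beta are lost instead. The immunoglobulin entry, listed between PHA and TREC, would also fall below the primary assays. SAP 8.3.2.2 summarizes those levels alongside a secondary endpoint, so its rank should be stated deliberately.
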